5.4. DEFINITION

Table 3 : Definitions

Term	Definition
Investigational Device (ID)	Perceval valve is a bioprosthetic heart valve made of bovine pericardium, stabilized in a buffered glutaraldehyde solution and assembled on a nitinol stent. The device is indicated for the replacement of a damaged or malfunctioning native heart valve in humans via traditional surgery.
Study Day Count	The day of implant is defined as study Day 1. Calculate the study day according to the following rules: If date < study Day 1 then study day = Date – study Day 1 If date > study Day 1 then study day = Date – study Day 1 +1
Baseline	Last preoperative assessment
Screening Failure	Screened patients who do not fulfill IE criteria OR patient who signed the IC but withdrawn from the study for termination reason is “Failure to meet randomization criteria”
Study completers	Patients who complete 5 year visit. The termination reason is “Completed the Study”
As-treated principle	Patients will be assigned to the treatment groups according to the device actually implanted to the subject.
As-randomized principle	Patients will be assigned to the treatment groups according to the randomization list independently from the actual implant to the device under investigation.

Term	Definition
Study phases	
 • Screening & enrolment • Operative evaluation • Hospital Discharge 
Assessments at:
 
 • 1 month (M1): 30 days \pm 7 days. The information (EQ5D) should be submitted to the site during the 1-3 months visit. • 1 to 3 months FU visit (M3): between 30 and 90 days • 1 year FU visit (Y1): 1 year (365 days) \pm 30 days after the day of the surgery • 2 years FU visit (Y2): 2 years (730 days) \pm 30 days after the day of the surgery • 3 years FU visit (Y3): 3 years (1095 days) \pm 30 days after the day of the surgery • 4 years FU visit (Y4): 4 years (1460 days) \pm 30 days months after the day of the surgery • 5 years FU visit (Y5): 5 years (1825 days) \pm 30 days after the day of the surgery

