10.4.3 SAFETY POPULATION

Safety population will include all randomized and implanted subjects evaluated based on the treatment actually received.

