Myocardial infarction	
Periprocedural MI (72 h after the index procedure)
 
 ○ New ischemic symptoms (e.g., chest pain or shortness of breath), or new ischemic signs (e.g., ventricular arrhythmias, new or worsening heart failure, new ST-segment changes, hemodynamic instability, new pathological Q-waves in at least 2 contiguous leads, imaging evidence of new loss of viable myocardium or new wall motion abnormality) AND ○ Elevated cardiac biomarkers (preferable CK-MB) within 72 h after the index procedure, consisting of at least 1 sample postprocedure with a peak value exceeding 153 as the upper reference limit for troponin or 53 for CK-MB.* If cardiac biomarkers are increased at baseline (>99th percentile), a further increase in at least 50% postprocedure is required AND the peak value must exceed the previously stated limit 
Spontaneous MI (>72 h after the index procedure):
 
 ○ Detection of rise and/or fall of cardiac biomarkers (preferably Troponin) with at least 1 value above the 99th percentile URL, together with myocardial ischemia as evidenced by at least 1 of the following: ○ Symptoms of ischemia ○ ECG changes indicative of new ischemia [new ST-T changes or new left bundle branch block (LBBB)] or New pathological Q-waves in at least 2 contiguous leads ○ Imaging evidence of a new loss of viable myocardium or new wall motion abnormality ○ Sudden, unexpected cardiac death, involving cardiac arrest, often with symptoms suggestive of myocardial ischemia, and accompanied by presumably new ST elevation, or new LBBB, and/or evidence of fresh thrombus by coronary angiography and/or at autopsy, but death occurring before blood samples could be obtained, or at a time before the appearance of cardiac biomarkers in the blood. ○ Pathological findings of an acute myocardial infarction"

Table 9 Primary endpoint definitions and classifications

Clinical Endpoint	Definition /Classification [1]
Valve reintervention	
Any surgical or percutaneous interventional catheter procedure that repairs, otherwise alters or adjusts, or replaces a previously implanted prosthesis or repaired valve (i.e. after surgical closure of index valve implantation).
 
Note: Additional interventions performed during the index valve implantation procedure before surgical closure are not considered re-interventions.

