2.4. RANDOMIZATION

Subjects are randomly assigned in equal numbers (1:1) to one of two treatment arms:

- Perceval valve
- Standard sutured stented bioprosthetic aortic valve (control)

on the basis of a randomization list that has been performed before study start. Randomization list is stratified by 2 factors:

- country, and
- surgical approach (full sternotomy” or “mini-sternotomy”).

Only subjects who have undergone standard chest CT-scan to determine if the aortic stenosis can be replaced with an available Perceval valve, and is potentially suitable for mini-sternotomy, may be randomized. For each subject the randomization will be performed through eDC system after enrollment and before valve operation, specifically after CT scan and surgical approach (“full sternotomy” or “mini-sternotomy”) has been determined.

One patient will be considered adherent to the randomization if an attempt to implant of the allocated valve is performed. In case of, after an unsuccessful implant, a valve of the other arm is implanted the adherence to randomization allocation will be considered maintained.

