6.2. SAFETY ANALYSIS POPULATION

The “Safety” population (SAF) is defined as all randomized and implanted patients. The SAF population will be used mainly for safety summaries. Patients will be allocated to the treatment groups according to the «as-treated» principle.

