13.1.2. Adverse Events Incidences

The incidence of AE is defined as the number of subjects with occurrence of this AE during the period of interest. The incidence rate (CIR for crude incidence rate) of an AE is defined as the number of subjects with occurrence of this AE during the period of interest divided by the total number of subjects n in the respective group (e.g., treatment group).

The incidence, incidence rate, the number of events and the percentage of events (related to the total number of events) will be summarized by AE term over the entire study post-implant period (from Day 1) and during the early and late phases (section 18.12). For the late events, the incidence rate will be calculated on the number of late patients only.

In addition, safety summaries will be done according to the following plan:

- Intraprocedural and periprocedural (within 72 hours) serious adverse events regardless of relationship with the device.

- All valve and procedure relevant (according to CEC adjudication) serious adverse event composite endpoints and their components as specified in VARC-2 guidelines (and reported in section 18.12):
 - Early safety at 30 days
 - Clinical efficacy after 30 days
 - Time related valve safety annually up to 5 years
- Serious device related (according to CEC adjudication) adverse events up to 5 years (from day 1 up to Day 1826)
- Postoperative site-reported unexpected serious adverse device effect (USADE)
- Site-reported relationship to procedure, device, drug/medication, or other Protocol Required Assessment (section 18.12)
- All late serious adverse events will be analyzed according to a constant hazard model: the linearized rates will be calculated as:
 - total number of late events divided by the total time under evaluation after 30 days (late patient-years).
 - number of patients with at least one late event divided by the total time under evaluation after 30 days (late patient-years).
- The incidence, incidence rate, the number of events and the percentage of Pacemaker (PM) implantation according to:
 - time of occurrence (overall, early, late and up to 1 year), and
 - relationship to device and procedure.

In addition, time-to-event methods (section 5.2) will be used to summarize the time to onset of the following events:

- deaths (overall, cardiovascular, and non-cardiovascular),
- explants and
- all main cardiovascular SAEs:
 - Bleeding,
 - SVD,
 - endocarditis,
 - valve thrombosis,
 - thromboembolic events,
 - stokes,

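### The Safety set groups patients by the valve implanted, so early harm after a failed first implant is counted in the other arm, and a bail-out to a non-study valve has no arm

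*SAP*

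**What the plan says.** SAP 5.4 (Table 3) defines the as-treated principle: "Patients will be assigned to the treatment groups according to the device actually implanted to the subject". SAP 6.2 applies it to the Safety set, "Patients will be allocated to the treatment groups according to the «as-treated» principle", and gives that set its role: "The SAF population will be used mainly for safety summaries". Protocol 10.4.3 is worded a little differently: "Safety population will include all randomized and implanted subjects evaluated based on the treatment actually received".

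The SAP foresees conversions. SAP 2.4 says that if "after an unsuccessful implant, a valve of the other arm is implanted the adherence to randomization allocation will be considered maintained". That sentence settles adherence to randomisation. No sentence settles the arm of such a patient in SAF.

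Two early safety endpoints fall in the window where a failed implant would do harm. One is in SAP 13.1.2: "Intraprocedural and periprocedural (within 72 hours) serious adverse events regardless of relationship with the device". The other is the 30-day early safety composite in SAP 18.12. Protocol 11.4 (Table 9) adds that "Additional interventions performed during the index valve implantation procedure before surgical closure are not considered re-interventions", so a second valve placed before chest closure is not a re-intervention event.

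SAP 6.6 (Table 4) marks adverse events for the enrolled, SAF and mITT sets, and the cost-effectiveness analyses (surgical times and consumption indices) for SAF and mITT. The mITT set is analysed as randomised and requires a study valve (SAP 6.4). Protocol 10.1.5 requires serious adverse events by arm in the enrolled, ITT and Safety populations. Table 4 has no ITT column, although SAP 3.1 reports no change from the protocol.

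**The concern.** The 72-hour and 30-day endpoints are meant to show the harm of implanting each valve. When a first valve fails and the other arm's valve is placed in the same operation, bleeding, stroke, kidney injury or death in the following days may come from the failed attempt. Grouping by the implanted valve puts those events in the column of the valve that rescued the operation. If conversions run mainly from Perceval to stented, the main safety table is biased in Perceval's favour.

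Two further effects follow from the same rule. The long clamp and bypass times of converted operations enter the control mean in the SAF version of the surgical-time analysis, which tests whether Perceval is faster. And a patient whose failed attempt ends with a non-study valve has an implant date, so belongs to SAF, but the rule gives that patient neither arm.

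**Working it through.** **Step 1. Where each patient goes.** Apply SAP 5.4, 6.2 to 6.4 and 18.12 to a patient in whom the randomised valve is attempted first:

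| Course of the operation | SAF | mITT | ITT |
|---|---|---|---|
| Perceval fails, stented valve placed | Control | Perceval | Perceval |
| Stented valve fails, Perceval placed | Perceval | Control | Control |
| First valve fails, non-study valve placed | In the set, no arm defined | Not in the set | As randomised |
| No valve implanted | Not in the set | Not in the set | As randomised |

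**Step 2. Inputs.** Per arm n = 617 (maximum 1234, allocated 1:1; Protocol 8.1 and 8.5.7). The documents give no conversion rate for this trial. The only implant-failure figure found is a cited multicentre series in Protocol 6.2: 1 failure in 314, and 313/314 = 99.7%, as printed. Scaled to one arm this is 617/314 = 1.96, about 2 patients (0.32%). Everything else is assumed and shown as a range: background risk r of an early serious adverse event (5 to 10%), risk q in converted patients (25 to 50%), conversions from Perceval to stented only, and equal background risk in both arms.

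**Step 3. Formula.** With k conversions and c = k/n, the risk difference (Perceval minus control) is:
- as randomised: [(n−k)r + kq]/n − r = c(q−r)
- as treated: r − (nr + kq)/(n+k) = −c(q−r)/(1+c)
- swing between the two: about 2c(q−r)

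**Step 4. Results, in percentage points.**

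| Conversions | r, q | As randomised | As treated | Swing |
|---|---|---|---|---|
| 2 (0.32%) | 10%, 25% | +0.05 | −0.05 | 0.10 |
| 2 (0.32%) | 5%, 50% | +0.15 | −0.15 | 0.29 |
| 19 (3.1%) | 10%, 25% | +0.46 | −0.45 | 0.91 |
| 19 (3.1%) | 5%, 50% | +1.39 | −1.34 | 2.73 |

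A wider range for q (20 to 60%, with r = 10%) gives 2 × 0.003 × 0.10 = 0.06 to 2 × 0.003 × 0.50 = 0.30 points at 0.3% conversions, and 0.6 to 3.0 points at 3%.

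In counts, suppose 19 conversions carry 10 events. As randomised, the table shows 40/617 (6.5%) against 31/617 (5.0%). In SAF it shows 30/598 (5.0%) against 41/636 (6.4%). Fisher's p is 0.33 in both.

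**Step 5. Surgical times.** If a converted operation has clamp time t and the arm means are otherwise mP and mC, SAF grouping moves the difference in Perceval's favour by about c(t−mP) + c(t−mC). One retrospective comparison in Protocol 6.3 reports mean clamp times of 26 and 58 minutes. As an illustration only, take t as their sum, 84 minutes. Then (84−26) + (84−58) = 84, and the shift is 0.0032 × 84 = 0.3 minutes at 2 conversions and about 0.031 × 84 = 2.6 minutes at 19, against a difference of 32 minutes in that study.

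**The case against.** The strongest reply is that SAF is not the only safety comparison. The mITT adverse-event tables keep a converted patient in the randomised arm, and the protocol requires ITT tables as well, so any distortion in SAF would show up as disagreement between planned tables. This stands, but only in part: SAF is the named main set, mITT drops non-study bail-outs, and the SAP has left the ITT set out of Table 4.

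A second reply is that safety is summarised descriptively (SAP 13), the primary analysis is on the per-protocol set, its mITT sensitivity analyses are as randomised, and the events committee judges each event's relation to device and procedure. This also stands, and no success criterion rests on the SAF safety tables. It does not cover everything. SAP 13.1.2 applies time-to-event methods, which under SAP 5.2 include log-rank p-values, to deaths, bleeding and strokes. The surgical-time superiority tests are marked for SAF and mITT, and SAP 12.1 does not say which of the two decides.

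A third reply is that the protocol's wording for the Safety set could include a valve that was attempted. That is arguable, but SAP 5.4 narrows it to the valve implanted.

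Three stronger readings are tempting and not supported:
- That conversions go uncounted. SAP 7.1 reports crossovers, non-study devices and patients not implanted, and SAP 8.3 reports implantation outcome and number of valves used.
- That SAP 2.4 already makes the attempt the exposure for safety. It defines adherence to randomisation only.
- That the safety conclusion would be reversed. With exactly equal background risk, any single conversion with q above r changes the sign, however trivially. More generally, the sign changes only if the as-randomised excess is smaller than roughly the swing.

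**Conclusion.** The point holds as a misattribution in the main safety table, and its likely size is small. On the SAP's own definition, early serious adverse events of a converted patient are tabulated under the valve that replaced the failed one, and a non-study bail-out has no arm in SAF. The swing is about 2c(q−r): roughly 0.06 to 0.3 points at 1 failure in 314, and about 1 to 3 points only if conversions reach around 3%. The documents neither support nor exclude that rate. The figures assume one-directional conversion and a higher event risk in converted patients; conversions in both directions would partly cancel. The shift in surgical times is also small under the illustration above.

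**What to change.** In SAP Table 3, 6.2 and 13.1.2:
- Group implanted SAF patients by the first valve attempted for intra-procedural, 72-hour and 30-day endpoints, and for surgical times where SAF is used. Include patients who end with a non-study valve.
- Keep grouping by the valve implanted for late device-related and time-related valve-safety endpoints.
- List the early serious adverse events of converted patients separately.

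In SAP Table 4, add the ITT column for serious adverse events that Protocol 10.1.5 requires. This also captures patients who receive no valve. They should not be added to SAF, because Protocol 10.4.3 limits that set to implanted patients.

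The cost is SAP wording, a second grouping variable in the safety tables and a derived variable for first valve attempted. Before committing, check the eCRF: the first-attempt item used in SAP 18.12 asks whether the randomised valve was implanted, and the documents do not show whether it separates an attempt that failed from one never made.

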6. ANALYSIS POPULATION

6.1. ENROLLED ANALYSIS POPULATION

The “Enrolled population” (ENR) is defined as all patients who will be included in the study (enroll date but no screening failure) with a signed and dated informed consent. The ENR population will be used mainly for subject disposition summaries.

6.2. SAFETY ANALYSIS POPULATION

The “Safety” population (SAF) is defined as all randomized and implanted patients. The SAF population will be used mainly for safety summaries. Patients will be allocated to the treatment groups according to the «as-treated» principle.

6.3. INTENTION-TO-TREAT ANALYSIS POPULATION

The “Intention-To-Treat” population (ITT) is defined as all randomized patients. Patients will be allocated to the treatment groups according to the «as-randomized» principle.

6.4. MODIFIED INTENTION-TO-TREAT ANALYSIS POPULATION

The “modified Intention-To-Treat” population (mITT) is defined as all randomized patients (ITT population) who receive a study valve (Perceval or standard sutured stented valve). Patients will be allocated to the treatment groups according to the «as-randomized» principle. The mITT population will be used as sensitivity efficacy analyses.

6.5. PER-PROTOCOL POPULATION

The “Per-Protocol” population (PP) is defined as all randomized and implanted patients attending the scheduled follow-up visits up to 1 year at minimum and without the following major protocol deviations:

- Assessment/Procedure (related to primary endpoint) Incomplete/Not Done
- Serious Adverse Event Not Reported
- No adherence to randomization allocation
- No consent obtained or if consent obtained after implant.

Further major protocol deviation may be detected by the Steering Committee and appropriately reported in the eCRF. In the exceptional event that “other” reasons requiring exclusion from the PP become apparent during the final data review, these will be suitably documented at that time in the final data review report (which will be prior to database lock).

Primary efficacy analysis will be performed on this population. The PP population will be used for analyses of primary and secondary endpoints.

